5.1.2.4. Entheses

After the imaging of all patients is completed, Elementary lesions of enthesitis will be defined and scored as per the GRAPPA US working group's definitions, as used in the multicenter DUET study (Table 2):⁴

All of the elementary lesions will be assessed for their presence or absence. In addition, some of the lesions will also be scored for their severity using a semi-quantitative system (grade 0 to 3). The definitions of each grade are outlined below.

Table-2:Probes/scanners, views and anatomical sites for enthuses assessment

Anatomical site	Views	GE Logic E9/S8	Clarius L15	Clarius L20
Achilles tendon insertions	posterior	X	X	X
Supraspinatus tendon insertions	lateral	X	X	
Triceps tendon insertions	posterior	X	X	
Common extensor tendon origins	lateral	X	X	
Quadriceps tendon insertions	anterior	X	X	
Patellar ligament (origin and insertion)	anterior	X	X	
Plantar fascia insertions	plantar	X	X	
Extensor digitorum tendon insertions at DIP and PIP	dorsal	X		X

The following sonographic enthesal lesions should be scored:

- **Hypoechoicity:** Distinct loss of homogenous fibrillar pattern with relative hypoechoicity compared to the rest of the enthesis after correcting for anisotropy.

Grade 0: Absent

Grade 1: Present

- **Thickening:** Increased thickness of the tendon/ligament at the enthesis compared to its body. Thickness may be difficult to judge and should be suspected when accompanied by other enthesal lesions.

Grade 0: Absent

Grade 1: Present

- **Bone Erosion:** A cortical defect confirmed with a step-down contour defect detected in two planes at the insertion of the tendon/ligament to the bone.

Grade 0: Absent

Grade 1: Present

- **Enthesophyte:** A step-up bony prominence at the normal bone contour. Grade the severity of the enthesophyte based on its length. Although the readers are not expected to measure the length of the enthesis we provided suggested cut off points to guide the grading of the enthesophytes

Grade 0: No enthesophytes

Grade 1: Small enthesophyte

Grade 2: Medium enthesophyte

Grade 3: Large enthesophytes

- **Calcification:** Hyperechoic linear structures detected within the tendon/ligament at the insertion to the bone but with no congruency with the bone.

Grade 0: No calcifications

Grade 1: Punctate hyperechoic area

Grade 2: Linear calcification without acoustic shadow

Grade 3: Egg-shell calcification with posterior acoustic shadow

- **Doppler Signal:** The presence of positive Doppler signal at the enthesis, confirmed in two perpendicular planes and distinguished from reflection of surface artifacts and nutritional vessel signal.

The intensity of the Doppler signal at the enthesis will be graded using a semi-quantitative score.

Note: We will consider any Doppler signal at the enthesis area including signals appearing beyond 2 mm of the bony cortex.

We will score the intensity of the Doppler signal on a semi quantitative grading system:

Grade 0: No Doppler signal

Grade 1: A single confluent Doppler signal or up to 3 discrete Doppler spots

Grade 2: Doppler signal affecting less than half of the enthesis

Grade 3: Doppler signal covering more than half of the enthesis

In addition, the location of each Doppler signal will be recorded:

Zone 1: ≤ 2 mm from the bone cortex

Zone 2: > 2 mm from the bone cortex

5.1.3. Safety Outcomes

Adverse events will be recorded during scanning.

5.2. Analysis Methods

Demographic, clinical and disease characteristics of patients will be presented using descriptive statistics. Numeric data showing normal distribution will be shared with mean and standard deviation, and those without normal distribution will be shared with median and interquartile range. Categorical data will be shared with numbers and percentages.

The primary endpoint analysis will be the interrater agreement of detecting any synovitis in B mode with the Clarius and gold standard machine. The kappa coefficients will be evaluated using the guideline outlined by Landis and Koch, where the strength of the kappa coefficients are: 0.01-0.20 slight; 0.21-0.40 fair; 0.41-0.60 moderate; 0.61-0.80 substantial; 0.81-1.00 almost perfect.⁷

For secondary outcomes, the interrater agreement for the presence of Doppler signals within the joints, tenosynovitis, erosions, nail, as well as features of enthesitis (hypoechoicity, thickening, erosions, enthesophytes, calcifications) will also be evaluated using the same method. The agreement of the semiquantitative grading of the intraarticular findings' severity (synovitis in B mode, Doppler signals, erosions, each being on a scale between 0-3) will be done using weighted kappa analysis.⁸

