1.2. Objectives

Our aim to test the concurrent validity of the Clarius handheld US devices versus gold-standard device to detect characteristic features of healthy and rheumatic joints (i.e. anatomical structures and vascular flow.

Primary objective:

To determine whether handheld US devices (Clarius HD3 L20 and L15 scanners) B mode are as accurate as gold standard device (GE Logic E9/S8) at visualizing intraarticular synovitis

Secondary objectives:

1. To determine whether handheld US devices (Clarius HD3 L20 and L15 scanners) power Doppler mode are as accurate as gold standard device (GE Logic E9/S8) at detecting intrasynovial signals
2. To determine whether handheld US devices (Clarius HD3 L20 and L15 scanners) B mode are as accurate as gold standard device (GE Logic E9/S8) at visualizing tenosynovitis
3. To determine whether handheld US devices (Clarius HD3 L20 and L15 scanners) power Doppler mode are as accurate as gold standard device (GE Logic E9/S8) at detecting intratendineous signals
4. To determine whether handheld US devices (Clarius HD3 L20 and L15 scanners) B mode are as accurate as gold standard device (GE Logic E9/S8) at visualizing bone erosions
5. To determine whether handheld US devices (Clarius HD3 L20 and L15 scanners) B mode are as accurate as gold standard device (GE Logic E9/S8) at grading intraarticular synovitis
6. To determine whether handheld US devices (Clarius HD3 L20 and L15 scanners) power Doppler mode are as accurate as gold standard device (GE Logic E9/S8) at grading intrasynovial signals
7. To determine whether handheld US devices (Clarius HD3 L20 and L15 scanners) B mode are as accurate as gold standard device (GE Logic E9/S8) at grading bone erosions
8. To determine whether handheld US devices (Clarius HD3 L20 and L15 scanners) power Doppler mode are as accurate as gold standard device (GE Logic E9/S8) at visualizing elementary lesions of enthesitis

9. To determine whether handheld US devices (Clarius HD3 L20 and L15 scanners) power Doppler mode are as accurate as gold standard device (GE Logic E9/S8) at detecting entheseal signals
10. To determine whether handheld US devices (Clarius HD3 L20 and L15 scanners) B-mode are as accurate as gold standard device (GE Logic E9/S8) at detecting trilaminar appearance of the nail plate abnormalities

2. Study Methods

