2.2. Randomization and Blinding

Study patients will not be randomized to any group. The same anatomical regions will be evaluated with the same ultrasound protocol for each patient included in the study. The scoring of the US images will be done blindly by the principal investigator at OHRI as stated below.

At the central site (OHRI), the research assistant will give a unique identifier number to each image, for a random quality control and for cross referencing whenever needed. The cropped images, as detailed below, will not have the subject ID visible to the PI at the time of reading but will be accessible for the quality control. (read-only access). The research assistant at OHRI is the only site personnel who has the capacity to uncrop the images in the PowerPoint file (password protected files).

Images will not contain any identifiable information such as Date of Birth (DOB) or initials. The US images will be transferred to a PowerPoint file by the research assistant at OHRI in JPEG format. The research assistant will generate an unblinded master list, inaccessible to other site personnel, to link the slide numbers with the patients and scanned anatomical sites and the slide will have no other information on the patient number or ID. For scoring the images by the PI, a random order slide show will be conducted, irrespective of the machine used or the anatomical site or patient assessed, to ensure blindness to data related to the

patient identifiers (The PI will not be blinded to the machine that the image was taken with as the JPEG format that is achieved from different machines are identifiable, but due to the random order scoring, images that belong to the same joint by the different machines are not to be scored consecutively). There will be nine separate powerpoint files, for images of joints, tendons, entheses, nail including power Doppler and gray scale findings; and grey scale file for erosions.

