2.3. Sample Size

Study agreement analyses will be done per joint. To give a kappa ≥ 0.61 (from substantial interrater agreement to almost perfect agreement) with a confidence interval width of 0.15 and the expectation of approximately 20 % of joints assessed having any synovitis in B mode (based on a previous study by our group), 683 joints would be required.⁴ This corresponds to 30 patients if 24 joints per patient are assessed. Non-inferiority margin will be $\kappa \geq 0.61$.

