2.4. Statistical Interim analyses and stopping guidance

An interim analysis will be done after 10 patients. In the interim analysis, the agreement between the images obtained with the handheld ultrasound and the images on the gold standard device will be compared after the blinded scoring. A moderate level of agreement (defined as a kappa value of >0.40) between the two tools in the interim analysis will allow parallel initiation of subsequent studies proposed in the research framework. The results of this interim analysis will not be used to adjust the design of the remainder of the study. We do not have any formal stopping rules for the trial.

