3.1. Confidence Intervals and P-values

We will consider $p < 0.05$ statistically significant for our outcomes. Results will be presented with their values with the 95% confidence interval.

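### The primary objective asks about accuracy against the GE machine, but the only planned primary analysis is kappa, which does not show the direction of disagreement

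*SAP*

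**What the plan says.** - **Objective.** SAP 1.2 and Protocol 3.0 name the GE Logic E9/S8 as the gold standard. The primary question is whether the Clarius L20 and L15 "B mode are as accurate as gold standard device (GE Logic E9/S8) at visualizing intraarticular synovitis".
- **Aim.** SAP 1.2 also words the purpose as agreement: "Our aim to test the concurrent validity of the Clarius handheld US devices versus gold-standard device".
- **Primary analysis.** SAP 5.2, and Protocol 4.4 in the same terms: "The primary endpoint analysis will be the interrater agreement of detecting any synovitis in B mode with the Clarius and gold standard machine". Kappa is read on the Landis-Koch bands. Other binary lesions get the same method, and graded joint findings get weighted kappa.
- **Criterion.** SAP 2.3 and Protocol 4.5 size the study for kappa of at least 0.61, with "the expectation of approximately 20 % of joints assessed having any synovitis in B mode". For the same value they write "Non-inferiority margin will be" kappa of 0.61 or more.
- **Estimate or limit.** Neither document says whether 0.61 applies to the estimate or to its lower confidence limit. The interim threshold in SAP 2.4 is worded as a value: "A moderate level of agreement (defined as a kappa value of >0.40". SAP 3.1 says: "Results will be presented with their values with the 95% confidence interval".
- **Reader.** One investigator scores all images. SAP 2.2: "The PI will not be blinded to the machine that the image was taken with".

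No section plans sensitivity, specificity, a 2x2 table or a paired comparison of positive rates for any lesion. The numbers and percentages promised in SAP 5.2 sit in the paragraph on patient characteristics.

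**The concern.** An accuracy question against a reference has two error rates: reference-positive joints scored negative, and reference-negative joints scored positive. Kappa combines them and is unchanged if the two counts are swapped. A probe that finds clearly less synovitis than GE and one that finds clearly more can reach the same kappa. Because the target is labelled a non-inferiority margin, either could be reported as showing equal accuracy. For a point-of-care detection tool the two errors have different consequences, and the planned output would not tell them apart. Weighted kappa for the grades, with the usual symmetric weights, has the same limit.

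**Working it through.** **Inputs from the documents.** Prevalence 20%, target kappa 0.61, interval width 0.15, 683 joints, 30 patients x 24 joints (SAP 2.3); 95% intervals (SAP 3.1). Joints per probe follow from SAP Table 1. L20: 8 sites x 2 sides = 16 per patient, 480 in 30 patients. L15: 6 x 2 = 12, 360 in all. Both counts are before exclusions under SAP 5.3.

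**Assumptions.** Specificities and the intra-patient correlation (ICC, 0 to 0.30), because the documents give neither; 20% prevalence within each probe's joint set, because the documents give it only overall.

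**Formulas.** With p the GE-positive share, s sensitivity and sp specificity against GE: both positive = p·s; GE-positive only b = p(1-s); handheld-positive only c = (1-p)(1-sp); both negative = (1-p)·sp. Kappa = (po - pe)/(1 - pe).

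**1. The plan's own figure.** Take equal positive rates on both devices, b = c = 0.0624. Then po = 0.8752, pe = 0.2² + 0.8² = 0.68 and kappa = 0.1952/0.32 = 0.61. The Fleiss-Cohen-Everitt variance is 0.9999 per joint, so n = (2 x 1.96/0.15)² x 0.9999 = 682.9. The 683 joints are reproduced. This case has balanced disagreement, with s = 0.688 and sp = 0.922.

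**2. 0.61 as a point estimate.**

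| s / sp (%) | po | pe | kappa | Handheld positive rate | Difference from GE (points) |
|---|---|---|---|---|---|
| 50 / 100 | 0.900 | 0.740 | 0.615 | 10.0% | -10.0 |
| 52 / 99 | 0.896 | 0.733 | 0.611 | 11.2% | -8.8 |
| 62 / 95 | 0.884 | 0.702 | 0.611 | 16.4% | -3.6 |
| 70 / 92 | 0.876 | 0.678 | 0.615 | 20.4% | +0.4 |
| 100 / 80 | 0.840 | 0.584 | 0.615 | 36.0% | +16.0 |

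On 720 joints, 144 of them GE-positive, the first, fourth and last rows mean 72 GE-positive joints scored negative with 0 errors the other way; about 43 and 46; and 0 and about 115. All three give kappa 0.615.

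**3. 0.61 as the lower 95% limit.** Solve kappa - 1.96 x SE x √DE = 0.61, with DE = 1 + (m - 1) x ICC and m = 16 or 12. Share of GE-positive joints scored negative:

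| Probe, ICC | sp 100% | sp 95% | sp 92% |
|---|---|---|---|
| L20, 0 | 41% | 28% | 20% |
| L20, 0.10 | 36% | 22% | 14% |
| L20, 0.30 | 31% | 16% | 8% |
| L15, 0 | 40% | 26% | 18% |
| L15, 0.10 | 36% | 22% | 14% |
| L15, 0.30 | 30% | 16% | 8% |

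At specificity 85% the share is at most 2% without clustering, and the criterion cannot be met at ICC 0.10. At 80% it cannot be met at any sensitivity, because kappa itself peaks at 0.615.

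**4. What the added measures could show.** The half-width of the paired difference is 1.96 x √[(b + c - (b - c)²)/n] x √DE. In points, at ICC 0 / 0.10 / 0.30, at the exact solutions of kappa = 0.61:

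| s / sp (%) | Difference | L20 | L15 |
|---|---|---|---|
| 52 / 99 | -8.8 | 2.8 / 4.4 / 6.5 | 3.2 / 4.6 / 6.7 |
| 57 / 97 | -6.2 | 2.9 / 4.6 / 6.8 | 3.4 / 4.9 / 7.0 |
| 62 / 95 | -3.6 | 3.0 / 4.8 / 7.1 | 3.5 / 5.1 / 7.3 |

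Zero is excluded throughout at 52/99, up to ICC 0.10 at 57/97, and only without clustering at 62/95.

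Near s = 0.69, the half-width for sensitivity is 1.96 x √(0.69 x 0.31/npos) x √[1 + (npos/30 - 1) x ICC]. For ICC 0 to 0.30 it is 0.09-0.12 for L20 (96 GE-positive joints) and 0.11-0.13 for L15 (72).

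**The case against.** - **Kappa fits the stated aim.** This stands. Concurrent validity is an agreement question, and kappa does fall as GE-positive joints are scored negative. A reader might infer that kappa is the wrong primary statistic; the documents do not support that.
- **The extreme pairs are unlikely.** 50/100 needs no error in the GE-negative joints and 100/80 none in the GE-positive ones. Nothing in the documents predicts either, and the case that reproduces 683 joints is balanced. This stands too: the pairs show what the criterion permits, not what is expected.
- **GE-positive joints scored negative are not proven misses.** GE status is one reader's score. If that reader's own repeat kappa were 0.80 (assumed), with equal positive rates, each discordant cell would be 0.20 x 0.2 x 0.8 = 0.032. That is 0.032/0.20 = 16% of positives changing on re-reading the same image. So 16%, the low end at specificity 95-100%, could be reader variation alone.
- **The machine-aware reader.** A reader might infer that knowing the machine will bias the scores one way. The documents show the possibility, not the bias.
- **Per-probe samples.** SAP 5.2 speaks of the Clarius without a stated split by probe. The 480 and 360 joints follow from SAP Table 1, not from a stated analysis set.
- **Limited gain.** The added analysis shows marked one-sidedness but may not show a mild one.

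None of these points supplies the missing direction of disagreement.

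**Conclusion.** The gap is real, and it is one of completeness. The planned primary output can support a claim of agreement, but it does not by itself answer the accuracy question in the primary objective. At 20% prevalence and with assumed specificities, a kappa estimate of 0.61 or more is compatible with a handheld positive rate anywhere from about 10% to 36%. Under the stricter lower-limit reading, the share of GE-positive joints scored negative can still be 16-41% at specificity 95-100% and 8-20% at 92%, for the per-probe joint counts and ICC 0-0.30. A reader might take 16-41% as a general figure, but it holds only under those assumptions and shrinks as specificity falls. Nor do the documents show that either probe performs at any of these values. The point should be fixed before the final analysis, because measures chosen after the results are known would carry less weight.

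**What to change.** Keep kappa as the primary analysis. In SAP 5.2:

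1. Prespecify, for L20 and L15 separately, the 2x2 counts, sensitivity and specificity against GE, and the paired difference in positive rate. Give 95% intervals that allow for clustering by patient, for example a bootstrap that resamples patients.
2. Do the same for the other binary lesions, with counts only where GE-positive sites are few. Each tendon site and the nails give at most 30 x 2 = 60 sites per device.
3. State that kappa of 0.61 or more supports a claim of agreement only, and that any statement of equal accuracy must be read with these estimates.
4. State that the estimates are relative to the GE score of one reader who is not blinded to machine, so they combine device difference, reader variation and possible bias.

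No new success threshold is added.

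**Cost.** No new data, visits or patients; a little more analysis and a few more table rows. Per-probe sensitivity will be precise only to about ±0.09 to 0.13 (20% prevalence assumed in each joint set). Mild one-sidedness may go undetected once clustering is allowed for, estimates for rare lesions may be unstable, and the accuracy conclusion becomes more cautious.

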5.3. Missing Data

If there are missing images for some sites for any of the probes, the images that were obtained for the same site using other probe(s) will also be excluded. The number of missing joint/tendon/enthesis and nail images will be reported. Missing data will not be imputed.

6. References

2-Filer A, de Pablo P, Allen G, Nightingale P, Jordan A, Jobanputra P, Bowman S, Buckley CD, Raza K. Utility of ultrasound joint counts in the prediction of rheumatoid arthritis in patients with very early synovitis. *Ann Rheum Dis*. 2011 Mar;70(3):500-7. doi: 10.1136/ard.2010.131573. Epub 2010 Nov 29. PMID: 21115552; PMCID: PMC3033529.

8-Cohen J, Weighed kappa: Nominal scale agreement with provision for scaled disagreement or partial credit. *Psychological Bulletin*.1968, 70 (4): 213–220

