4.3 Ultrasound Protocol (Assessment of Joints and Enthesis)

Each patient will have consecutive (same day) US examinations using the Clarius handheld and GE gold-standard devices. All scans will be performed in a darkened room. Power Doppler settings will be standardized with a pulse repetition frequency of 500 Hz and low wall filters. The colour gain will be increased to the highest value where power Doppler signals under the bony cortex are not generated. There will be no further training for this step as the 3 investigators have done multiple research projects together and separately, with reproducibility being tested and presented.¹⁵ However, there will be a investigators meeting prior to data collection to review all anatomical sites, positioning and standard views and agree on labelling. All images will be labeled to identify anatomical site and laterality. A glossary will be provided for labelling, to ensure blinding in the later stages. At least one B mode and one power Doppler image will be saved for each site and lesion. The standard will be saving the images in longitudinal views. Transverse views will be saved if there is an abnormality noted on the long axis.

Representative images will be collected and saved for all of the following structures bilaterally:

Joints (24 total): 2nd-3rd metacarpophalangeal (MCP), 2nd-3rd proximal interphalangeal (PIP), 2nd-3rd distal interphalangeal (DIP), wrist, elbow, shoulder, knee, ankle and 5th metatarsophalangeal (MTP) joints of the foot, bilaterally. For the MCP, PIP and DIP joints, if joints other than the 2nd or 3rd present with swelling (e.g. 4th or 5th) they will be scanned instead. This approach is to ensure a maximum number of swollen joints will be assessed.

Entheses (20 total):

Large entheses: Supraspinatus, triceps, common extensor tendon, quadriceps, patellar ligament (origin and insertion), Achilles tendon, Plantar fascia insertions;

Small entheses: extensor digitorum tendon insertion at the DIP and PIP level

Tendons (4 total): Extensor digitorum tendon of the second digits, tibialis posterior tendon in the ankles

Nail: In case of having a nail PsO, the most involved nail and contralateral side will be assessed. If there is no nail PsO, procedure will be performed on the nail of the 2nd digit of the hands.

All study procedures and that will take place in one study visit, as summarize in Table-1.

Table-1: Assessment schedule

Procedures	Visit 1
Obtain informed Consent	x

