Inclusion/Exclusion criteria	x
Demographics	x
Relevant medical history	x
Current Psoriatic Arthritis treatment	x
Pain VAS	x
Patient global assessment	x
HAQ-DI	x
Disease activity (66/68 joint count)	x
SPARCC enthesitis index	x
Dactylitis count	x
BSA	x
Presence of nail disease	x
Ultrasound protocol using both machines	x
Documentation of the ESR and CRP (if already done as standard of care)	x
Adverse event collection	x

VAS: Visual Analogue Scale; HAQ-DI: Health Assessment Questionnaire Disability Index; SPARCC: Spondloarthritis Research Consortium of Canada; BSA: Body Surface Area; ESR: Erythrocyte Sedimentation Rate; CRP: C-reactive protein

Scanners/probes that will be used for each anatomical site is summarized in Table-2.

Table-2: Probes/scanners, views and anatomical sites

Anatomical site	Views	GE Logic E9/S8	Clarius L15	Clarius L20
2 nd MCP joints	dorsal and lateral	X	X	X
3 rd MCP joints	dorsal	X		X
2 nd -3 rd PIP, 2 nd -3 rd DIP	dorsal	X		X
Wrist	dorsal	X	X	X
5 th MTP joints	dorsal and lateral	X		X
Elbow joints	posterior	X	X	
Shoulder joints	posterior	X	X	
Knee joints	anterosuperior	X	X	
Ankle joints	anterior	X	X	
Nails	dorsal	X		X
Achilles tendon insertions	posterior	X	X	X
Supraspinatus tendon insertions	lateral	X	X	
Triceps tendon insertions	posterior	X	X	
Common extensor tendon origins	lateral	X	X	
Quadriceps tendon insertions	anterior	X	X	
Patellar ligament (origin and insertion)	anterior	X	X	

Plantar fascia insertions	plantar	X	X	
Extensor digitorum tendon insertions at DIP and PIP	dorsal	X		X
Extensor digitorum tendon of the second digits	dorsal	X		X
Tibialis posterior tendon	medial	X	X	

MCP: metacarpophalangeal; PIP: proximal interphalangeal; DIP: distal interphalangeal (DIP); MTP: metatarsophalangeal

Subject ID: Every study subject will be given unique study ID. This will consist of site ID and patient number respectively (Site IDs will be 01 for OHRI, 02 for Women College and 03 for University of Florida).

Labelling: During the ultrasound scan every image that is saved will be given a label by the local research assistant.

Exporting: After each scan, all the images of each study subject will be exported in JPEG format. The images will be saved in a file with the subject ID, which will be unique. This file will be sent to the central site (OHRI) using Sharepoint by the local research assistant.

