5.1. Outcome Definition

5.1.1. Primary Outcome

After the imaging of all patients is completed, intraarticular synovitis scoring will be done based on the OMERACT definitions (scales of 0-3) as follows, for the anatomical sites given in Table 1.^{5,6}

Greyscale inflammatory (hypoechoic) synovial hyperplasia:

Grade 0: no hypoechoic synovial hyperplasia

Grade 1: minimal hypoechoic synovial hyperplasia (filling the angle between the periarticular bones, without bulging over the line linking tops of the bones)

Grade 2: hypoechoic synovial hyperplasia bulging over the line linking tops of the periarticular bones but without extension along the bone diaphysis

Grade 3: hypoechoic synovial hyperplasia bulging over the line linking tops of the periarticular bones and with extension to at least one of the bone diaphysis

Table-1:Probes/scanners, views and anatomical sites for primary outcomes

Anatomical site	Views	GE Logic E9/S8	Clarius L15	Clarius L20
2nd MCP joints	dorsal and lateral	X	X	X
3rd MCP joints	dorsal	X		X
2nd-3rd PIP, 2nd-3rd DIP	dorsal	X		X
Wrist	dorsal	X	X	X
5th MTP joints	dorsal and lateral	X		X
Elbow joints	posterior	X	X	
Shoulder joints	posterior	X	X	
Knee joints	anterosuperior	X	X	
Ankle joints	anterior	X	X	

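### The missing-image rule discards usable GE–handheld pairs at the three-probe sites (a small loss), and no breakdown of missing images by probe or reason is specified

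*SAP*

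**What the plan says.** SAP 5.3 (Missing Data) is triggered when a site lacks an image from any of the probes. In that case "the images that were obtained for the same site using other probe(s) will also be excluded". It adds that "The number of missing joint/tendon/enthesis and nail images will be reported" and that "Missing data will not be imputed".

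SAP Table 1 ("Probes/scanners, views and anatomical sites for primary outcomes") and SAP Table 2 ("Probes/scanners, views and anatomical sites for enthuses assessment") show which probe images which site; Protocol Table 2 agrees. All three probes are marked at the 2nd MCP, the wrist and the Achilles insertion. Every other joint and enthesis has GE plus one handheld.

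The primary analysis (SAP 5.2) is the agreement between Clarius and the gold-standard machine on any B-mode synovitis. Neither document describes an analysis that needs L15 and L20 images of the same joint.

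Protocol 4.3 requires that "At least one B mode and one power Doppler image will be saved for each site and lesion", and states that "every image that is saved will be given a label by the local research assistant". It also allows finger joints to be swapped: "if joints other than the 2nd or 3rd present with swelling (e.g. 4th or 5th) they will be scanned instead".

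**The concern.** There are two separate effects.

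**(a) Intact pairs are deleted.** If only the L15 image of a wrist is missing, the GE and L20 images of that wrist still form a complete pair, but the rule removes them. The reverse holds if only L20 is missing. The cost is precision, with no stated analysis that benefits. At sites with one handheld probe an incomplete pair cannot be used in any case, so the rule is not at fault there.

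**(b) A failed acquisition is handled like a lost file.** The objectives ask whether the handhelds visualize lesions as accurately as GE. A site that GE imaged and the handheld could not is relevant to that question. The rule takes such a site out of kappa, and the only reporting the SAP commits to is a count by type of structure. If such failures occur and are related to synovitis or to disagreement, the kappa from complete pairs could be biased. If they are unrelated to both, it is not. A poor image that was saved is still scored and still counts, so this concerns only sites with no saved handheld image.

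**Working it through.** **1. The plan's own figure.** Inputs from SAP 2.3 and 3.1: kappa k = 0.61, prevalence p = 0.20, full interval width 0.15, 95% confidence. The large-sample variance of kappa, with the same prevalence on both devices and independent joints, is V/n, where

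V = (1−k)[(1−k)(1−2k) + k(2−k)/(2p(1−p))] = 0.9999.

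Then n = 4 × 1.96² × V / 0.15² = 682.9, so 683. The planned figure is reproduced, and the same formula is used for the widths below.

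**2. Pairs per patient (SAP Table 1, both sides).**
- L15: 2nd MCP, wrist, elbow, shoulder, knee, ankle = 6 × 2 = 12.
- L20: 2nd and 3rd MCP, two PIP, two DIP, wrist, 5th MTP = 8 × 2 = 16.
- Joints with both handhelds: 2nd MCP and wrist = 4. Check: 12 + 16 − 4 = 24 joints.
- For 30 patients: 360 + 480 = 840 pairs, of which 8 × 30 = 240 are at three-probe joints.

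Counting GE–L15 and GE–L20 as separate pairs is an assumption of this check. The plan does not say how the two handhelds are combined where both are used.

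**3. Avoidable loss under (a).** Let q be the share missing per probe, independent across probes. The documents give no rate, so q is assumed. A pair is lost needlessly when its own two images exist and the third is missing: 240·q·(1−q)². Otherwise valid pairs: 840·(1−q)².

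| q | Pairs lost | Valid pairs | Share | L15 CI width | L20 CI width |
|---|---|---|---|---|---|
| 1% | 2.4 | 823.3 | 0.3% | 0.2087 → 0.2090 | 0.1807 → 0.1809 |
| 5% | 10.8 | 758.1 | 1.4% | 0.2175 → 0.2193 | 0.1883 → 0.1895 |
| 10% | 19.4 | 680.4 | 2.9% | 0.2295 → 0.2335 | 0.1988 → 0.2013 |

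The largest widening is 0.0039 (L15, 10%).

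If each joint counts once (720 planned), the joints kept under the rule and under per-pair deletion are 644 and 655 at 5% (width 0.154 and 0.153), and 574 and 593 at 10% (0.164 and 0.161).

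For the Achilles, 30 × 4 × q(1−q)² gives 1.2, 5.4 and 9.7 of 660 enthesis pairs at 1%, 5% and 10%.

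Finger-joint swapping can shrink the loss. If both 2nd MCPs were always replaced, and the substitutes scanned with L20 only (an assumption), there would be 780 pairs with 120 at three-probe joints. The loss would be 120q/780 = 0.15%, 0.8% and 1.5%.

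**4. How far (b) could move kappa.** This is an illustration, not an estimate of bias. Start from complete pairs with kappa 0.61 and 20% positive on both devices (cells 0.1376, 0.0624, 0.0624, 0.7376). Add a share f of sites that GE imaged and the handheld could not, of which a share s are GE-positive.

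| f (assumed) | Scored handheld-negative, s from 0 to 1 | Scored as disagreement, any s |
|---|---|---|
| 1% | 0.611 to 0.587 | 0.587 |
| 3% | 0.613 to 0.544 | 0.543–0.544 |
| 5% | 0.615 to 0.503 | 0.501–0.503 |

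At f = 0.5% the disagreement bound is 0.599, and at 0.1% it is 0.608. Handheld-negative scoring raises kappa when fewer than about 4% of the failed sites are GE-positive, because it credits the device with agreement at joints it did not image.

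**The case against.** **Part (a) changes little.** This stands. The re-estimated widths barely move, and most of the loss at any missing rate is unavoidable. The reserve of 720 − 683 = 37 joints is used up at about 2.4% missing per probe under the rule and at about 2.8% under per-pair deletion. A reader might infer that the rule endangers the sample size; the figures do not support that.

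**A common joint set has some value.** Keeping L15 and L20 on the same joints at shared sites is a reasonable complete-case choice in a study of two scanners. But the plan states no L15-versus-L20 comparison, and the two probes' site sets already differ by design.

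**The SAP does not forbid a breakdown.** A reader might infer that reporting is restricted to counts by structure. The text does not say so; it is only silent on probe and reason. The probe can largely be worked out from labels, the master list and the recognisable image format. The reason might emerge from the centre query (Protocol 8.0) or the protocol-violation records (SAP 3.2). Labels, however, attach only to saved images, and neither procedure requires a reason for a missing image to be recorded or reported.

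**Failures may be rare or absent.** This also stands. The protocol requires images of every site, SAP 3.2 requires full compliance, and missing data are queried. A reader might take the kappas of 0.50 to 0.54 as the likely size of a bias. They rest on assumed outright failure rates of 3% to 5% and on extreme scoring, and the documents suggest no such rates. Nor do they support the inference that the rule flatters the handheld.

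**Conclusion.** The point holds as a minor one that the sponsor could adopt. On its plain wording SAP 5.3 deletes usable GE–handheld pairs at the 2nd MCP, wrist and Achilles, and no stated analysis needs that deletion. The precision cost is negligible to small over the range checked. It rests on assumed missing rates, independence of missingness across probes, joints treated as independent (as the plan does), and separate L15 and L20 pairs.

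The reporting gap is the more substantive half, because a handheld-only failure bears on the study question and no breakdown is specified that would show it. Whether such failures occur, how often, and which way they would move kappa cannot be established from the documents. Confidence is high in the reading of the rule and in the arithmetic, but not in any consequence of the reporting gap.

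**What to change.** 1. Reword SAP 5.3 so that a GE–handheld pair is excluded only when one of its own two images is missing: GE–L15 if GE or L15 is missing, GE–L20 if GE or L20 is missing. State at the same time how L15 and L20 results are combined or kept apart at the shared sites.
2. Report missing images by probe and, where known, by reason: not acquired or lost, versus attempted but not obtainable. Use the CRF, or the existing query to the centre, to collect the reason.
3. Keep the complete-pair kappa as the primary result, without imputation.
4. Only if some sites were obtained on GE and not obtainable on the handheld, add a sensitivity range that counts those sites as handheld-negative and, as the conservative bound, as disagreements. Handheld-negative alone is not enough, for the reason shown in step 4 of the working. State this as an exception to the no-imputation sentence.

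The cost is a change of SAP wording, a small CRF or query addition, and one table. The L15 and L20 estimates would rest on slightly different joints at the shared sites. For patients already scanned, reasons may be known only in retrospect.
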